### 5.3 Exclusion criteria

Patients eligible for this study must not meet **any** of the following criteria:

1. HER2-overexpressing patients by local laboratory testing (IHC 3+ staining or in situ hybridization positive), based on the most recent test. Note: Patients with IHC 2+ must have a negative in situ hybridization test.
2. Patients who received more than one chemotherapy line for ABC

Note: A chemotherapy line in advanced disease is an anticancer regimen that contains at least one chemotherapy agent and is given for 21 days or longer. If a cytotoxic chemotherapy regimen was discontinued for a reason other than disease progression and lasted less than 21 days, then this regimen does not count as a "prior line of chemotherapy". Chemotherapy regimens composed of more than one drug are considered as one line of therapy.

3. Patient with symptomatic visceral disease and is candidate to chemotherapy
4. Patients with only non-measurable lesions other than lytic or mixed (lytic and blastic) bone metastasis (e.g. pleural effusion, ascites etc.)
5. Previous treatment with exemestane, mTOR inhibitors, PI3K inhibitors, AKT inhibitors.
6. Known hypersensitivity to mTOR inhibitors, e.g. sirolimus (rapamycin)
7. Patients who have a history of another primary malignancy, with the exceptions of non-melanoma skin cancer, and carcinoma in situ of the cervix, uteri, or breast who have been disease free for  $\geq 3$  years

8. Radiotherapy within four weeks prior to enrollment in the study except in case of localized palliative radiotherapy (for analgesic purpose) or for lytic lesions at risk of fracture which was completed at least two weeks prior to registration in the current study. Patients must have recovered from radiotherapy toxicities.
9. Currently receiving any hormone replacement therapy, unless discontinued prior to registration in the current study.
10. Patients with central nervous system (CNS) involvement unless they meet ALL of the following criteria:
  - At least 4 weeks from prior therapy completion (including radiation and/or surgery) to starting the study treatment.
  - Clinically stable CNS lesions at the time of screening which are untreated or without evidence of progression for at least 4 weeks after treatment, as determined by clinical examination and brain imaging (MRI or CT). Patients must not be treated with steroids for brain metastases during the screening period
11. Patients receiving concomitant immunosuppressive agents or chronic corticosteroids use at the time of study entry except topical applications, inhaled sprays, eye drops or local injections.
12. Bilateral diffuse lymphangitic carcinomatosis
13. Severely impaired lung function as defined as spirometry and DLCO that is 50% or less of the normal predicted value and/or O2 saturation that is 88% or less at rest on room air
14. Patients who have serious liver disease such as cirrhosis, decompensated liver disease, and acute or currently active hepatitis (i.e. quantifiable HBV-DNA and/or positive HbsAg, quantifiable HCV-RNA)
15. Patients with a known history of HIV seropositivity. Screening for HIV infection at baseline is not required.
16. Active, bleeding diathesis, or on oral anti-vitamin K medication (except low dose warfarin, LMWH and acetylsalicylic acid or equivalent, as long as the INR is  $\leq 2$ ).
17. Impairment of gastrointestinal (GI) function or GI disease that may significantly alter the absorption of study treatment.
18. Uncontrolled diabetes mellitus as defined by HbA1c  $>7\%$  despite adequate therapy. Patients with a known history of impaired fasting glucose or diabetes mellitus (DM) may be included, however, blood glucose and antidiabetic treatment must be monitored closely throughout the trial and adjusted as necessary;
19. Active ulceration of the upper gastrointestinal tract.
20. Any severe and / or uncontrolled medical conditions such as
  - a. unstable angina pectoris, symptomatic congestive heart failure, myocardial infarction  $\leq 6$  months prior to randomization, serious uncontrolled cardiac arrhythmia,
  - b. active or uncontrolled severe infection,
21. Patients being treated with drugs recognized as being strong inhibitors or inducers of the isoenzyme CYP3A4 (Rifabutin, Rifampicin, Clarithromycin, Ketoconazole, Itraconazole, Voriconazole, Ritonavir, Telithromycin) continuously for at least 7 days during any time period in the last 2 weeks prior to registration in the current study

22. Patients who have received live attenuated vaccines within 1 week of start of study drug and during the study. Patient should also avoid close contact with others who have received live attenuated vaccines. Examples of live attenuated vaccines include intranasal influenza, measles, mumps, rubella, oral polio, BCG, yellow fever, varicella and TY21a typhoid vaccines;
23. History of noncompliance to medical regimens
24. Patients unwilling to or unable to comply with the protocol
25. Patients who are currently part of or have participated in any clinical investigation with an investigational drug within 1 month prior to dosing

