
	
disease, and acute or currently active hepatitis (i.e. quantifiable HBV-DNA and/or positive HbsAg, quantifiable HCV-RNA)
 
15. Patients with a known history of HIV seropositivity. Screening for HIV infection at baseline is not required.
 
16. Active, bleeding diathesis, or on oral anti-vitamin K medication (except low dose warfarin, LMWH and acetylsalicylic acid or equivalent, as long as the INR is <math>\leq 2</math>).
 
17. Impairment of gastrointestinal (GI) function or GI disease that may significantly alter the absorption of oral everolimus.
 
18. Uncontrolled diabetes mellitus as defined by HbA1c <math>>7\%</math> despite adequate therapy. Patients with a known history of impaired fasting glucose or diabetes mellitus (DM) are eligible, however blood glucose and antidiabetic treatment must be monitored closely throughout the trial and adjusted as necessary;
 
19. Active ulceration of the upper gastrointestinal tract.
 
20. Any severe and / or uncontrolled medical conditions such as
 
 
a. unstable angina pectoris, symptomatic congestive heart failure, myocardial infarction <math>\leq 6</math> months prior to randomization, serious uncontrolled cardiac arrhythmia,
 
b. active or uncontrolled severe infection,
 
 
21. Patients being treated with drugs recognized as being strong inhibitors or inducers of the isoenzyme CYP3A4 (Rifabutin, Rifampicin, Clarithromycin, Ketoconazole, Itraconazole, Voriconazole, Ritonavir, Telithromycin) continuously for at least 7 days during any time period in the last 2 weeks prior to registration in the current study
 
22. Patients who have received live attenuated vaccines within 1 week of start of study drug and during the study. Patient should also avoid close contact with others who have received live attenuated vaccines. Examples of live attenuated vaccines include intranasal influenza, measles, mumps, rubella, oral polio, BCG, yellow fever, varicella and TY21a typhoid vaccines;
 
23. History of noncompliance to medical regimens
 
24. Patients unwilling to or unable to comply with the protocol
 
25. Patients who are currently part of or have participated in any clinical investigation with an investigational drug within 1 month prior to dosing;

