#### Screening for hepatitis B

During the screening phase, all patients should be tested for hepatitis B viral load and serologic markers of HBV-DNA, HBsAg, HBsAb, and HBcAb.

Patients with positive hepatitis B results should start prophylactic antiviral treatment of 1 to 2 weeks prior to the first doses of the study treatment, and should continue for at least 4 weeks after last dose of study treatment.

The management guidelines, in [Section 6.3.2.3](#), are provided according to the results of the baseline assessment of viral load and serological markers for hepatitis B.

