## 6.3.2 Additional management and follow-up for selected toxicities

### 6.3.2.1 Management of infections

Everolimus has immunosuppressive properties and may predispose patients to bacterial, fungal, viral or protozoal infections, including infections with opportunistic pathogens. Localized and systemic infections, including pneumonia, other bacterial infections, invasive fungal infections, such as aspergillosis, candidiasis or pneumocystis jirovecii pneumonia (PJP) and viral infections including reactivation of hepatitis B virus, have been described in patients taking everolimus. Some of these infections have been severe (e.g. leading to sepsis, respiratory or hepatic failure) and occasionally have had a fatal outcome.

Physicians and patients should be aware of the increased risk of infection with everolimus. Treat pre-existing infections prior to starting treatment with everolimus. While taking everolimus, be vigilant for symptoms and signs of infection; if a diagnosis of infection is made, institute appropriate treatment promptly and consider interruption or discontinuation of everolimus.

Patients with positive results of HBV-DNA and/or HBsAg at screening should begin a prophylaxis treatment for 1-2 week prior to beginning everolimus therapy. Patients should have HBV-DNA monitored frequently throughout the course of everolimus therapy for signs of hepatitis reactivation.

If a diagnosis of invasive systemic fungal infection is made, discontinue everolimus and treat with appropriate antifungal therapy.

Cases of PJP, some with fatal outcome, have been reported in patients who received everolimus. PJP may be associated with concomitant use of corticosteroids or other immunosuppressive agents. Prophylaxis for PJP should be considered when concomitant use of corticosteroids or other immunosuppressive agents is required.

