**Table 6-5 Action to be taken based on hepatitis B screening results**

	Result	Result	Result	Result	Result
HBV-DNA	+	+ or -	-	-	-
HBsAg	+ or -	+	-	-	-
HBsAb	+ or -	+ or -	+ and no prior HBV vaccination	+ or -	- or + with prior HBV vaccination
HBcAb	+ or -	+ or -	+ or -	+	-
Recommendation	Prophylaxis treatment should be started 1-2 weeks prior to first dose of study treatment. Monitor HBV-DNA approximately every 4-8 weeks (from Visit 2 and onwards)	No prophylaxis Monitor HBV-DNA approximately every 4 weeks (from Visit 2 and onwards)			No specific action

Antiviral prophylaxis therapy should continue for at least 4 weeks after last dose of study treatment. For hepatitis B reactivation, definition and management guidelines see [Table 6-6](#).

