**Table 6-6 Guidelines for management of hepatitis B**

HBV reactivation (with or without clinical signs and symptoms)*	
For patients with baseline results: Positive HBV-DNA OR Positive HBsAg ----- Reactivation is defined as: [Increase of 1 log in HBV-DNA relative to baseline HBV-DNA value OR new appearance of measurable HBV-DNA]	Treat: Start a second antiviral AND Interrupt study treatment administration until resolution: - ≤ baseline HBV-DNA levels  If resolution occurs within 28 days, study treatment should be re-started at one dose lower, if available. (see Table 6-2 Study drug dose reductions) If the patient is already receiving the lowest dose of study drug according to the protocol, the patient should restart at the same dose after resolution. Both antiviral therapies should continue at least 4 weeks after last dose of study drug. If resolution occurs > 28 days, patients should discontinue study treatment but continue both antiviral therapies at least 4 weeks after last dose of study drug.
For patients with baseline results: Negative HBV-DNA and HBsAg AND [Positive HBsAb (with no prior history of vaccination against HBV), OR positive HBcAb] ----- reactivation is defined as: New appearance of measurable HBV-DNA	Treat : Start first antiviral medication AND Interrupt study drug administration until resolution: ≤ undetectable (negative) HBV-DNA levels If resolution occurs within 28 days, study drug should be re-started at one dose lower, if available. (see Table 6-2 Study drug dose reductions) If the patient is already receiving the lowest dose of study drug according to the protocol, the patient should restart at the same dose after resolution. Antiviral therapy should continue at least 4 weeks after last dose of study drug. If resolution occurs > 28 days, patients should discontinue study drug but continue antiviral therapy at least 4 weeks after last dose of study drug.

\* All reactivations of hepatitis B are to be recorded as grade 3 (CTCAE v4.03), unless considered life threatening by the investigator; in which case they should be recorded as grade 4 (CTCAE v4.03). Date of viral reactivation is the date on which the rise or reappearance of HBV- DNA was recorded.

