**Table 6-7 Guidelines for management of hepatitis C flare**

HCV flare *	
For patients with baseline results: Detectable HCV-RNA, HCV flare is defined as: > 2 log 10 IU/mL increase in HCV-RNA AND ALT elevation > 5 x ULN OR 3 x baseline level, whichever is higher	Discontinue study treatment
For patients with baseline results: Knowledge of past hepatitis C infection with no detectable HCV-RNA, HCV flare is defined as: New appearance of detectable HCV-RNA AND ALT elevation > 5 x ULN OR 3 x baseline level, whichever is higher	Discontinue study treatment
*All flares of hepatitis C are to be recorded as grade 3 (CTCAE v 4.03), unless considered life threatening by the investigator; in which case they should be recorded as grade 4 (CTCAE v 4.03). Date of viral flare is the date on which both the clinical criteria described above were met (e.g., for a patient whose HCV-RNA increased by 2 logs on 01 JAN 2011 and whose ALT reached > 5 x ULN on 22 JAN 2011), the date of viral flare is 22 JAN 2011.	

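### Exclusion 14 bars HBsAg-positive patients, yet later sections give instructions for treating them and waive waiting for the deciding results; Table 7-1 omits half the HBV-DNA tests recommended for eligible antibody-positive patients

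*Protocol*

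**What the plan says.** **Eligibility.** Criterion 14 in Protocol Section 5.3 excludes "acute or currently active hepatitis (i.e. quantifiable HBV-DNA and/or positive HbsAg, quantifiable HCV-RNA"; the Protocol summary has the same definition ("i.e. quantifiable HBV-DNA and/or positive HbsAg, quantifiable HCV-RNA"). HBsAg is named without a threshold, while HBV-DNA and HCV-RNA must be quantifiable. Sections 4.1 (Screening phase), 5.1, 6.5.2 and 7.1.2.1 make randomization and dosing conditional on all criteria being met, with the check built into the IRT.

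**Management.** Section 6.3.2.1 says "Patients with positive results of HBV-DNA and/or HBsAg at screening should begin a prophylaxis treatment for 1-2 week prior to beginning everolimus therapy". For the HBV-DNA-positive and HBsAg-positive columns, Table 6-5 says "Prophylaxis treatment should be started 1-2 weeks prior to first dose of study treatment". Table 6-6 opens with "For patients with baseline results: Positive HBV-DNA OR Positive HBsAg" and, on reactivation, instructs "Start a second antiviral AND Interrupt study treatment administration until resolution", with a restart one dose lower if resolved within 28 days. Section 4.1 is less specific: "Patients with positive hepatitis B results should start prophylactic antiviral treatment of 1 to 2 weeks prior to the first doses", with no marker singled out. Table 6-7 covers hepatitis C: "For patients with baseline results: Detectable HCV-RNA, HCV flare is defined as".

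**Waivers.** Section 6.3.2.4 allows the first dose before the screening HBV result in a patient with known chronic HBV who takes anti-HBV medication. It allows the same for the HCV result in known chronic HCV, with no medication condition. Section 7.1.2.3 gives a waiver for either virus but ties it to anti-HBV medication.

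**Monitoring.** For patients negative for HBV-DNA and HBsAg but positive for HBcAb, or for HBsAb without vaccination, Table 6-5 recommends no prophylaxis and HBV-DNA about every 4 weeks from Visit 2. Table 7-1 places hepatitis monitoring, where it applies, at screening, every 2 cycles after C1D1, and end of treatment. It has no numbered visits.

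**The concern.** A site with an HBsAg-positive patient reads in one place that she cannot enter, and in others how to prepare her for the first dose and manage her on treatment. The waivers concern the patients most likely to fail criterion 14, and they release the site from waiting for the result that decides it.

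The monitoring gap affects patients who are properly eligible. They receive no prophylaxis, and Table 6-6 starts an antiviral and interrupts study drug in them only when HBV-DNA newly appears, so the test interval sets how late that response can be. Section 6.3.2.1 lists hepatitis B reactivation among the infections described with everolimus. Scheduled chemistry follows the same every-2-cycle visits, so routine ALT and AST give no earlier signal.

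**Working it through.** **1. Eligibility against management, by screening result**

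| Screening result | Criterion 14 | Later sections | Reading |
|---|---|---|---|
| HBsAg positive | Excluded | Prophylaxis (6.3.2.1, Table 6-5); reactivation rules (Table 6-6) | Direct conflict |
| HBV-DNA positive, HBsAg negative | Excluded only if quantifiable | Same rules, triggered by a positive result | Overlap; a detectable but unquantifiable patient is eligible on a literal reading and needs these rules |
| HCV-RNA detectable | Excluded only if quantifiable | Flare rules (Table 6-7) | As above |
| HBV-DNA and HBsAg negative, HBcAb positive or unvaccinated HBsAb positive | Eligible | No prophylaxis, HBV-DNA about 4-weekly (Table 6-5) | No eligibility conflict; see step 3 |

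The protocol does not relate quantifiable, positive and detectable to each other, so the conflict is exact for HBsAg only. It cannot be explained by later conversion, because Section 6.3.2.1 refers to screening results and Table 6-6 to baseline results.

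**2. Waivers against the eligibility checks**

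- Section 6.3.2.4, HBV: known chronic HBV and on anti-HBV medication.
- Section 6.3.2.4, HCV: known chronic HCV, no medication condition.
- Section 7.1.2.3: chronic HBV or HCV, and on anti-HBV medication.

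Each permits dosing before a result that criterion 14 depends on. Section 4.1 requires all criteria to be verified, Section 6.5.2 randomizes only patients who fulfil them, and Section 7.1.2.1 checks eligibility after screening is complete. A site cannot use the waiver and also meet those three.

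**3. Monitoring interval**

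Inputs: the visit-day formula in SAP 2.7.2, ((X − 1) × 4) × 7 + 1 for Cycle X Day 1; the every-2-cycle column of Table 7-1; the 4-week interval of Table 6-5.

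- X = 3: 2 × 4 × 7 + 1 = Day 57. X = 5: 4 × 4 × 7 + 1 = Day 113. Both match the SAP's stated days. X = 7: 6 × 4 × 7 + 1 = Day 169.
- Table 7-1 interval: 113 − 57 = 56 days. Table 6-5 interval: 4 × 7 = 28 days.
- Scheduled tests to week 24 in a patient still on treatment: 24/8 = 3 against 24/4 = 6, if the first 4-weekly test is at week 4 (assumption, because Visit 2 is undefined; 7 if it means Day 1).
- Missing draws: weeks 4, 12 and 20, so 3.

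The prophylaxis columns of Table 6-5 ask for testing about every 4 to 8 weeks. An 8-week schedule lies at the upper end of that range, so there is no mismatch for them.

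**4. Average number of extra draws (for cost only)**

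Assume treatment stops at an exponential PFS event with the medians of Protocol Section 10.6, at 30.4375 days per month (SAP 5.3). The medians are 4.1 × 30.4375 = 124.8 days and 6.6 × 30.4375 = 200.9 days. The share still on treatment at day t is 0.5^(t/median).

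- 4.1 months: days 28, 84, 140 give 0.856 + 0.627 + 0.460 = 1.94.
- 6.6 months: 0.908 + 0.748 + 0.617 = 2.27.

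So the change adds about 2 extra draws on average, and 3 for a patient still on treatment at week 24.

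**The case against.** The eligibility gate is strong. Four sections point the same way, the IRT check precedes the first medication number, and the management tables nowhere grant eligibility. A reader might infer that HBsAg-positive patients will be dosed. The documents do not support that: a site that follows Section 6.5.2 does not randomize a patient with a positive HBsAg. The instructions still contradict each other.

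The waivers cover only patients whose chronic infection is already known, and a site must still confirm the criteria in the IRT. They may be leftover text. That narrows the group but does not remove the contradiction. A reader might also take Section 7.1.2.3 as repeating the unconditional HCV waiver of Section 6.3.2.4. It does not, because it requires anti-HBV medication.

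On monitoring, Table 6-5 is a recommendation for a subgroup and Table 7-1 a general grid. Section 7.2.2.5 permits more frequent tests at the investigator's discretion, so a site can obey both. That is right: this is an omission from the schedule rather than a prohibition. But discretion does not schedule the draws, and limiting the row to patients for whom it applies adds no visits.

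Lastly, the HBsAg-positive row of Table 6-6 has a use. It is the only reactivation guidance for a carrier randomized in error or found after dosing, so it should not be deleted.

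**Conclusion.** The point holds in three limited parts.

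1. Criterion 14 and the prophylaxis and reactivation instructions conflict exactly for HBsAg-positive patients. Section 4.1 contributes only through its general reference to positive hepatitis B results. Extending the conflict to every HBV-DNA-positive or HCV-RNA-positive patient goes beyond the text, because the thresholds are worded differently.
2. The waivers in Sections 6.3.2.4 and 7.1.2.3 contradict the eligibility checks for a narrow group with known chronic infection.
3. For eligible antibody-positive patients without prophylaxis, Table 7-1 schedules HBV-DNA at 56 rather than 28 days: 3 tests by week 24 against about 6. The day counts follow from the stated schedules; the 6 assumes a first test at week 4. A reader might infer that all hepatitis B monitoring is too sparse, but the 4-to-8-week columns agree with Table 7-1.

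These should be fixed, but they do not threaten the trial's main result: estimation of PFS, the 110 events and the 160 patients are untouched. The documents give no reactivation rate and no size for the antibody-positive group, so the clinical impact is not quantified.

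**What to change.** 1. State in Sections 4.1 and 6.3.2.1 and in Table 6-5 that criterion 14 governs eligibility and that HBsAg-positive patients are not randomized. Use one threshold term for HBV-DNA and HCV-RNA throughout. Keep Tables 6-6 and 6-7 as management rules for eligible patients with a detectable but unquantifiable result, and for any carrier randomized in error or found after dosing.
2. Delete the sentences in Section 6.3.2.4 (HBV and HCV) and Section 7.1.2.3 that allow dosing before the screening results. Known carriers then wait for a local result within the existing 21-day screening window.
3. Add to Table 7-1 a 4-weekly HBV-DNA row for patients negative for HBV-DNA and HBsAg but positive for HBcAb, or for HBsAb without vaccination. Replace Visit 2 in Table 6-5 with a named visit; C2D1 (Day 29) is a suggestion. The 8-weekly row can stay for the others.

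The cost is amendment wording plus about 2 to 3 local draws per affected patient by week 24. The week 4 draw can use the Cycle 1 Week 4 PK visit, but should not move if the PK sample is postponed under Section 7.2.3. Weeks 12 and 20 have no scheduled visit, so up to two short laboratory visits are added.

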## 6 Treatment

### 6.1 Study treatment

The investigational drug used in the course of this trial is everolimus. In addition, all patients will receive open label exemestane. For this study, the term “Study treatment” is defined as everolimus + exemestane or placebo + exemestane. Study drug is defined as everolimus or matching placebo.

In both treatment arms, the study drug will be administered by continuous oral daily dosing of 2 × 5 mg tablets each morning. For the list of excipients, please refer to current [Investigator’s Brochure].

